**EXPANDED HEMODIALYSIS *VERSUS* ONLINE HEMODIAFILTRATION: A
PILOT STUDY ON INTRADIALYTIC HEMODYNAMICS AND FLUID STATUS**

Institution

Department of Medicine, Renal Division, University of São Paulo, São Paulo,
Brazil

NCT ID NCT03274518

Unique Protocol ID: 16928

Document Date: 09/27/2019

Abstract

Conventional hemodialysis (HD) is essential for the treatment of end-stage renal disease (ESRD) patients, by reducing serum concentration of uremic toxins and correcting fluid overload.

Nevertheless, HD removes almost exclusively low-range uremic toxins. Therefore, medium-range molecules, such as beta-2-microglobulin might accumulate in tissues, leading to many clinical complications, such as neuropathies, tendinopathies, anemia, bone mineral disease and reduced growth in children.

Convective methods might reduce incidence of these complications, by removing molecules of medium-range molecular weight. Online hemodiafiltration (oIHDF) is the most extensively used method in this regard. Nevertheless, there are some barriers to the wider introduction of this method in clinical practice, since specific machines are needed for this procedure, the costs with dialysis lines are higher and water consumption increases. More recently, the development of new membranes for hemodialysis allowed removal of medium- and high-range uremic toxins, with albumin retention. Thus, they allow removal of a broad range of uremic toxins, without changing dialysis machine or increasing water consumption. Such therapy is known as expanded hemodialysis (HDx).

The aim of this present study is to compare the extraction of middle-size molecules, the hemodynamic behavior, fluid and nutritional status of patients submitted to oIHDF or HDx, in a crossover study.

Introduction

End-stage renal disease (ESRD) is a condition characterized by marked decline in renal function, usually at rates below 10 ml/min/1.73 m². In Brazil, there are about 110,000 patients on maintenance hemodialysis (HD) and mortality rates are around 19%.⁽¹⁾ The explanation for this high mortality rate derives from comorbidities such as Diabetes Mellitus, arterial hypertension and left ventricular hypertrophy.⁽²⁻⁴⁾ Additionally, these patients are submitted to extracorporeal circulation, with intense body fluid variation and electrolyte composition during procedure. Besides, several uremic toxins are not removed during HD sessions.⁽⁵⁾

Improvement of dialysis and membrane technologies has flourished in the last decades. They have provided better management of these patients and prolonged survival.

Uremic syndrome

Uremic syndrome is characterized by several clinical manifestations resulting from the progressive loss of renal function, with biochemical, fluid and functional alterations.^(6, 7)

Uremic toxins have different molecular weights. The most frequently reported is urea, which has molecular weight of 60 Da and is used as a marker of HD quality. Low molecular weight solutes are readily dialyzable by conventional HD. Intermediate molecular weight (IMW) solutes have a molecular weight between 500 and 60000 Da. Among them are beta-2-microglobulin (β 2M), which is associated with dialysis-related amyloidosis, leptin, related to malnutrition, prolactin, which is associated to infertility of women in dialysis, hepcidin, related to the anemia of patients with CKD, among others.^(8, 9) IMW solutes are not significantly removed by conventional HD and tend to accumulate in the organism of dialytic patients.⁽¹⁰⁾ More recently, membranes for HD with high permeability to medium molecules and with selective retention of albumin have also emerged as an option to convective therapies. Such modality is known as expanded hemodialysis (HDx).⁽¹¹⁾

Online Hemodiafiltration

The oIHDF technique combines diffusion with high convection rates in which the dialysis fluid, free of toxins and pyrogens, is used to prepare the replacement fluid.(12)

The online module of dialysis machine prepares the replacement fluid by a cold sterilization process. There is a cross-flow water preparation, in order to avoid the accumulation of possible contaminants. The addition of bicarbonate and acid solutions to water follows the process. Next, the ready-for-infusion dialysis solution is passed through another ultrafilter prior to being infused into patients. The microbiological safety of these systems is demonstrated in clinical studies with an absence of activity-inducing cytokines and pyrogenic reactions.(13, 14)

Some studies have compared oIHDF with HD. The Contrast study(15) included 714 patients, with an average follow-up of 3 years. There were no differences in mortality in both modalities. However, for replacement volume above 21.95L, there was reduction in mortality of oIHDFol group. The Turkish study(16) also presented similar data, without differences in general mortality, with the exception of the subgroup of patients with a replacement volume greater than 17.4L.

The Eshol study,(17) which included 906 patients, with an average follow-up of 1.91 years, showed a reduction in mortality using oIHDF, regardless of the replacement volume used. In this study, mean replacement volume was 23.7L.

Dialysis membranes

Blood-dialysate interaction through semi-permeable membranes has always characterized dialysis methods since the first dialysis sessions in the mid-twentieth century.

Some physical characteristics determine the dialysis membranes:

- KoA: determines the permissibility to the diffusion of small molecules, in the presence of ideal diffusion conditions (with theoretically infinite blood and dialysate flows);

- Kuf: is determined by hydraulic conductance of a membrane in the presence of a transmembrane pressure;

- sieving: proportion of molecules that can cross the membrane, according to their molecular weight.

The diffusive process depends fundamentally on the density of pores in the membrane. The ultrafiltration and sieving properties vary depending on the mean pore diameter of the membrane.

The size of the pores determines which molecules are allowed to move across membranes. The molecular size at which the sieving coefficient is only 0.1 is termed membrane's cutoff value. That is, molecules with molecular weight above this value are unlikely to cross the membrane.

However, the cutoff value is not the only one that defines the permeability of a membrane. Another parameter, termed "retention onset" (RO) should also be determined for this purpose. It describes the molecular weight/radius where the sieving value is 0.9. Besides, dialysis membranes can have different pore sizes. Membranes with a more heterogeneous distribution of pore size may present greater loss of albumin than a membrane with more homogeneous sizes of these pores, although both have the same cutoff values.(11)

High cutoff membranes have recently been introduced into clinical practice, with the potential benefit of removing toxins with high molecular weight, typically associated with sepsis, rhabdomyolysis and hematological diseases, such as inflammatory cytokines, myoglobin, free light chains. Such membranes, however, also lead to loss of albumin, which can lead to or aggravate malnutrition.

More recently, membranes with high cutoff values, but with tight pore size distribution have been developed. The main concept is to keep both cutoff and retention onset values close to each other, but with a cutoff value lower than of albumin. This should allow removal of middle-to-high weight range uremic toxins, with very low albumin leak. Thus, these membranes, denominated high retention onset (HRO) membranes, allow performing both diffusive and convective processes in a conventional hemodialysis machine. These new HRO membranes defined a new modality of HD, denominated expanded hemodialysis (HDx).

Hypothesis

Our hypothesis is that HDx is noninferior to olHDF in the following parameters:

- Hemodynamic stability
- Nutritional and fluid status
- Removal of beta-2 microglobulin

Objectives

To evaluate each patient, through a prospective, randomized and cross-over study, the intradialytic hemodynamic behavior, fluid and nutritional status assessed by electrical bioimpedance and B2M removal in two dialytic modalities: HDFol versus HDx.

Subject and Methods

Inclusion criteria

Adult patients who are on maintenance HD at Hospital das Clínicas and agree to participate in the study by signing the informed consent form.

Exclusion criteria

Patients who cannot understand or who refuse to sign the informed consent form;
Patients who are currently on daily HD or olHDF.

Concise methods

a) Clinical and laboratorial data

Clinical data will be collected from the institution's chart, recorded and filled with all necessary precautions to keep confidentiality of patient's information. They are: baseline renal disease, age, history of smoking, sedentary lifestyle, presence of comorbidities such as hypertension and diabetes mellitus, family history of cardiovascular disease, history of coronary and cerebrovascular disease and medications.

Laboratory tests used to determine the biochemical, hematological and bone mineral profile characteristics will be obtained from routinely collected

exams. Such exams are processed by the Central Laboratory of Hospital das Clínicas / FMUSP.

b) Dialysis

All dialysis procedures will be performed by the Dialog+ Admea™ machine (BBraun Melsungen AG, Germany).

The oHDF will be prescribed as follows: blood flow 350 - 400 ml/min, dialysate flow 800 ml/min, post-dilution flow (90-100 ml/min), with high-flux Xevonta™ (BBraun Melsungen AG, Germany) or CAHP/DICE™ (Baxter Healthcare Corporation, Deutschland) dialyzers, with surface area of 1.7-2.4 m². The duration of each session will be from 3,5h to 4h, depending on current dialysis prescription. Total substitution volume will be higher than 20 L per session.

HDx will follow the same prescription of oHDF, regarding blood and dialysate flows and dialysis duration. There will be no substitution volume. Theranova™ dialyzers (Baxter Healthcare Corporation, Deutschland) will be used for each session.

Before initiating protocol and during the washout period, patients will be submitted to high-flux HD, which is the standard treatment in our service.

c) Hemodynamic monitoring

Cardiac output index (CI), stroke volume (SV - integrated mean of the flow waveform between the current upstroke and the dichotic notch), peripheral arterial resistance (PAR - ratio of mean arterial pressure to stroke volume multiplied by heart rate) and blood pressure (BP) will be accessed by finger beat to-beat monitor Finometer™ (Finapres Medical Systems BV, Arnhem, The Netherlands), within 15 minutes after starting oHDF or HDx sessions (predialysis) and again, 15 minutes before its end (post-dialysis), according to a previous studies of our group.(18-20).

d) Bioelectrical impedance

Segmental tetrapolar bioelectrical impedance (BIS) will be performed in all patients while recumbent, before starting study protocol and before each phase of the study (HDx or oHDF), by the multifrequency InBody™ S10

(Biospace Co., Ltd., Korea) device. It allows assessment of the following parameters regarding body fluids: total body water, total extracellular body water, lower limbs total water content, lower limbs extracellular water content. Additionally, α -angle, which is a marker of cellular integrity and nutritional status, will be noted.(21)

e) Blood and Effluent samples

Blood samples will be collected pre-session, mid-session and post-dialysis sessions, both in the first and last dialysis sessions of each of the periods studied (HDFol or HDx). Pre-session blood samples will be collected immediately after arteriovenous fistula puncture and the middle and post-session samples will be collected from the arterial line, 2 minutes after reduction of blood flow to 50 ml/min and suspension of dialysate flow and/or replacement.

In addition, partial and homogeneous collection of the effluent will be performed by a drainage hose, with an infusion pump operating continuously at a rate of 1l/h, as previously validated in the literature,(22-25) and successfully replicated by our service.(26, 27) The whole effluent of dialysis session will be collected.

Description of study design and procedures are described in figure 1. Blood and effluent samples to be collected are depicted in table 1.

[figure not shown]

Figure 1. Protocol description

Table 1. Description of Serum and effluent samples

Blood	First Sample (pre-dialysis)	Second Sample (mid-dialysis)	Third Sample (post-dialysis)
Albumin	X	X	X
β 2-microglobulin	X	X	X
Creatinin	X		X
Phosphorus	X	X	X
Hematocrit	X		
Hemoglobin	X		
Total Protein	X	X	X
Urea	X	X	X
Effluent			
Albumin		X	
β 2-microglobulin		X	
Phosphorus		X	
Urea		X	

Statistical Analysis

According to parametric distribution or not of the studied variables, paired t test or Wilcoxon's test will be used, respectively. The following variables will be compared in the two following situations HDFol *versus* HDx, HDFol *versus* high-flux HD and HDx *versus* high-flux HD:

- Pre-dialysis serum samples: albumin, β 2-microglobulin, creatinine, phosphorus, hematocrit, hemoglobin, total proteins, urea;
- Intradialytic serum samples: albumin, β 2-microglobulin, phosphorus, total proteins, urea;
- Post-dialysis serum samples: albumin, β 2-microglobulin, creatinine, phosphorus, total proteins, urea;
- Intradialytic effluent samples: albumin, β 2-microglobulin, phosphorus, total proteins, urea;
- Pre-dialysis hemodynamic variables: blood pressure, cardiac index;
- Post-dialysis hemodynamic variables: blood pressure, cardiac index, systolic volume, peripheral vascular resistance;
- Pre-dialysis bioimpedance variables: extracellular water / total body water ratio and α -angle;
- Post-dialysis bioimpedance variables: extracellular water / total body water ratio and α -angle.

References

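### The only stated hypothesis is noninferiority of HDx to olHDF, but the analysis plan gives only tests of difference, with no margin, confidence interval or decision rule

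*Combined protocol and SAP*

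**What the plan says.** The Hypothesis section contains one hypothesis: "Our hypothesis is that HDx is noninferior to olHDF in the following parameters". Three bullets follow: hemodynamic stability, nutritional and fluid status, and removal of beta-2 microglobulin. The Objectives section describes a randomized cross-over comparison and ties the second and third bullets to measurements: "fluid and nutritional status assessed by electrical bioimpedance and B2M removal in two dialytic modalities: HDFol versus HDx".

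The Statistical Analysis section names a single method: "According to parametric distribution or not of the studied variables, paired t test or Wilcoxon's test will be used, respectively". It then lists serum, effluent, hemodynamic and bioimpedance variables, to be compared between HDFol and HDx and between each of these and high-flux HD. One entry reads "Post-dialysis hemodynamic variables: blood pressure, cardiac index, systolic volume, peripheral vascular resistance".

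The visible text gives no noninferiority margin, confidence interval, significance level, sidedness, sample size or rule for declaring HDx noninferior.

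**The concern.** Noninferiority means that any deficit of HDx is smaller than a stated margin. A paired t or Wilcoxon test in its usual form asks whether the difference is zero. The two questions come apart in both directions:

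- A non-significant result is compatible with a large deficit measured imprecisely, so it does not support the hypothesis.
- A significant deficit may be too small to matter, so it does not refute the hypothesis.

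Only a significant result in favour of HDx would support the hypothesis, and that is a stronger claim than the one made. Followed exactly, the plan gives its only hypothesis no other means of support. If the gap were filled informally by treating p>0.05 as success, the conclusion would be easiest to reach where the study is least informative. That matters in a study whose title calls it a pilot.

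**Working it through.** **Inputs.** The documents give the hypothesis type (Hypothesis), the paired cross-over design (Objectives) and the tests (Statistical Analysis). They give no sample size, alpha, SD or margin, so there is no planned figure to reproduce. Everything below is an illustration on assumed values: two-sided alpha 5%, normally distributed paired differences, and margin M and true deficit d in units of the SD of the paired difference.

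**Step 1: chance that a treatment worse by the full margin gives p>0.05.** With n patients,

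P(|T| < t(0.975, n−1)), where T is noncentral t with n−1 degrees of freedom and noncentrality d√n, taking d = M.

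At n=20 the critical value is 2.093. The noncentralities are 0.25×√20 = 1.118, 0.5×√20 = 2.236 and 0.75×√20 = 3.354.

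| n | M = 0.25 SD | M = 0.5 SD | M = 0.75 SD |
|---|---|---|---|
| 10 | 89% | 71% | 44% |
| 20 | 81% | 44% | 11% |
| 30 | 74% | 25% | 2% |
| 40 | 66% | 13% | 0.4% |

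The result depends heavily on the assumed margin, so no single cell should be taken as the size of the problem.

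**Step 2: the same treatment under a confidence interval rule.** Suppose noninferiority is concluded only if the unfavourable bound of the two-sided 95% interval excludes M. The pass probability is 1 − F(t(0.975, n−1)), where F is the noncentral t distribution function with noncentrality (M−d)√n. At d = M the noncentrality is zero, so the probability is 2.5% at every n.

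**Step 3: what the rule would cost if the treatments are truly equal.** Put d = 0 and M = 0.5 SD. The Hypothesis names fluid and nutritional status separately, so full coverage means four criteria: hemodynamics, fluid, nutrition and beta-2 microglobulin removal. If the four are assumed independent, joint success is the fourth power of single success.

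| n | One criterion | All four |
|---|---|---|
| 10 | 29.3% | 0.293⁴ ≈ 0.7% |
| 16 | 46.5% | 0.465⁴ ≈ 5% |
| 20 | 56.4% | 0.564⁴ ≈ 10% |
| 30 | 75.4% | 0.754⁴ ≈ 32% |
| 40 | 86.9% | 0.869⁴ ≈ 57% |

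For at least 80% success, 34 patients are needed for one criterion and 53 for all four (0.9465⁴ = 0.803 at n=53). Positive correlation between the criteria would raise the joint figures.

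**The case against.** The strongest reply is that this is a pilot, that the abstract and Objectives speak of comparing and evaluating, and that the plan never says a non-significant test will count as noninferiority. All of this is true. A reader might infer that the sponsor intends to read p>0.05 as success, but the documents do not say so, and Step 1 applies only if someone does. Pilot status can also excuse low power. It does not supply a margin for a noninferiority hypothesis, and the aims do not withdraw that hypothesis.

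A reader might also infer that the endpoints are wholly undefined. That goes too far:

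- The Bioelectrical impedance section identifies the α-angle as a nutritional marker. The only other bioimpedance variable in the analysis list is the ratio of extracellular to total body water, which serves fluid status. Each construct thus has one analysed variable.
- The unfavourable direction for beta-2 microglobulin is evident, because the Abstract and the section on uremic syndrome describe harm from its accumulation.
- The visible text writes out no formula for removal, but the effluent method is cited to published work that cannot be consulted here. Whether those sources supply the calculation is unknown.
- Blood is sampled in the first and last session of each period, and the text does not say which carries the hypothesis. Figure 1, which is not shown, may bear on sessions and timing, though it is unlikely to contain a margin.

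What remains open on choice of variable is hemodynamics, where several measures are listed and none is designated.

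**Conclusion.** The point holds. The stated hypothesis and the planned tests do not match, and the visible text offers no valid route from the analysis to a noninferiority conclusion short of HDx being significantly better. This rests on the wording alone and on no assumed number.

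The size of the resulting error cannot be known, because the documents give no sample size, SD, alpha or margin. On the assumptions in the working, at n=20, treating p>0.05 as noninferiority would pass a treatment worse by the full margin between 11% and 81% of the time as the margin runs from 0.75 down to 0.25 SD, against 2.5% under the interval rule.

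**What to change.** **Preferred for a pilot.** Reword the hypothesis to estimation. In Statistical Analysis, report the HDx versus HDFol paired difference with a two-sided 95% confidence interval for each hypothesis variable, and state that p>0.05 will not be read as noninferiority. This changes wording only and needs no new patients or measurements.

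**If the noninferiority claim is kept.** Before outcome data are seen, the sponsor should fix a justified margin and an unfavourable direction for each of four constructs:

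- fluid status, by the extracellular to total body water ratio;
- nutritional status, by the α-angle;
- hemodynamic stability, by one designated variable;
- beta-2 microglobulin removal, as a calculated quantity with lower removal unfavourable.

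Noninferiority on a construct is concluded only when the unfavourable 95% bound excludes its margin, and the plan should say whether all four are required. If outcome data have already been seen, only the estimation wording remains open.

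**Cost.** The pilot may have to report that noninferiority was not established, which Step 3 shows is likely at small n even with equal treatments.

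A separate point needs reconciling: the Bioelectrical impedance section schedules measurements before the protocol and before each phase, while the analysis list includes "Post-dialysis bioimpedance variables: extracellular water / total body water ratio".

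### As the readable text stands, bioimpedance is timed only before the protocol and before each phase, which gives neither an on-treatment HDx/HDFol pair nor any post-dialysis reading for the planned comparisons

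*Combined protocol and SAP*

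**What the plan says.** The Objectives name bioimpedance as the measure for one of the study's questions: "fluid and nutritional status assessed by electrical bioimpedance and B2M removal in two dialytic modalities".

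Concise methods, section d, gives the only readable schedule for it: readings are taken "before starting study protocol and before each phase of the study (HDx or oHDF". It names no reading during a phase, at the end of a phase or after a session.

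Concise methods, section b, says what patients receive outside the study phases: "Before initiating protocol and during the washout period, patients will be submitted to high-flux HD".

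The Statistical Analysis opens its list with "The following variables will be compared in the two following situations HDFol" against HDx, and then each of the two against high-flux HD. The list includes "Pre-dialysis bioimpedance variables: extracellular water / total body water ratio" and "Post-dialysis bioimpedance variables: extracellular water / total body water ratio", each together with the α-angle.

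The other measures have on-treatment times in the prose. Section c takes hemodynamic readings "within 15 minutes after starting oHDF or HDx sessions (predialysis) and again, 15 minutes before its end (post-dialysis". Section e takes blood before, midway through and after sessions, "both in the first and last dialysis sessions of each of the periods studied (HDFol or HDx". Section e also refers the reader to Figure 1 for the design and procedures. The figure is not available in the text reviewed.

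**The concern.** A reading taken before a phase cannot reflect that phase's treatment. If the washout lies between the phases, the reading labelled HDx and the reading labelled HDFol both describe a patient on high-flux HD. Comparing them says nothing about how the two modalities differ in their effect on fluid or nutritional status. A reading before a phase also cannot serve as the reading after an HDx or HDFol session in that phase.

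The Hypothesis section states that HDx is noninferior to HDFol on nutritional and fluid status. A contrast held near zero by the timing of measurement would appear to support that hypothesis for a reason unrelated to treatment. On-treatment readings that were never taken cannot be recovered at analysis.

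**Working it through.** The plan gives no figure of its own to reproduce here. The check sets the schedule against the analysis list, then works out what the pre-phase contrast would estimate.

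**1. Timing of the HDFol versus HDx comparisons.** Counts come from the Statistical Analysis list, Table 1 and sections c to e. Effluent variables are left out.

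| Measure | Comparisons listed | On-treatment timing in the prose |
|---|---|---|
| Serum | 8 pre + 5 mid + 6 post = 19 | Section e: first and last session of each period |
| Hemodynamic | 2 pre + 4 post = 6 | Section c: near the start and the end of HDFol or HDx sessions |
| Bioimpedance | 2 pre + 2 post = 4 | Section d: none |

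Timing within a period does not by itself guarantee exposure: pre-session blood at the first session also precedes that period's treatment. Section e, however, samples the last session too, so an on-treatment pair exists for serum.

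**2. Readings needed and supplied.** The bioimpedance lines need HDx, HDFol and high-flux HD, each pre- and post-dialysis: 3 × 2 = 6 kinds of reading. With the washout between phases, section d supplies at most 1 (high-flux HD, pre-dialysis). It is at most 1 because section d does not say whether the reading precedes or follows a session.

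**3. What the labelled contrast estimates.** Let m be the level on high-flux HD and π the shift between the two pre-phase readings due to period alone. Let dF and dX be the effects of HDFol and HDx relative to high-flux HD, and D = dX − dF. Let LF and LX be the shares of those effects still present just before phase 2. None of these quantities is given in the documents.

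- Sequence HDFol then HDx: the reading labelled HDFol is m and the one labelled HDx is m + π + LF·dF. The difference HDx − HDFol is π + LF·dF.
- Sequence HDx then HDFol: the reading labelled HDx is m and the one labelled HDFol is m + π + LX·dX. The difference HDx − HDFol is −(π + LX·dX).
- Mean over balanced sequences: (LF·dF − LX·dX)/2.

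Results:

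- Complete washout (LF = LX = 0): the mean is 0 for any D.
- Equal residues (LF = LX = L): the mean is −(L/2)·D, which is −0.15·D at L = 0.3 and −0.25·D at L = 0.5.
- Unequal residues, for illustration LF = 0.5, LX = 0.1, dF = 0.2, dX = 0.7: (0.5 × 0.2 − 0.1 × 0.7)/2 = (0.10 − 0.07)/2 = +0.015, against D = 0.7 − 0.2 = +0.5.

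The contrast is therefore zero with complete washout. Otherwise it reflects carry-over, with a size and sign that the documents do not allow one to state.

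**4. If no washout lies between the phases.** The readable text does not say where the washout falls. Without one between the phases, the reading before phase 2 is on-treatment for the phase 1 modality, but it would be labelled with the phase 2 modality. Each patient then has an on-treatment reading for one modality only, so the paired HDx/HDFol comparison still cannot be formed.

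**The case against.** The strongest objection is Figure 1. The text refers to it for the design and procedures, and it is missing here only because figures did not survive conversion. It may hold on-treatment and post-session bioimpedance readings. A reader might infer that the plan has no such readings at all; the documents do not support that, and the point is limited to the readable text. The objection does not remove the conflict: if the figure has the timings, section d still states a narrower schedule, and staff could follow either.

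A second objection concerns the count. The bioimpedance lines give 12 comparisons (2 variables × 3 modality pairs × pre and post), and one might say that none of the 12 can be made. But 8 of them involve high-flux HD, and sections c and e do not time high-flux readings either. That gap is shared across the measures. The 4 HDFol versus HDx comparisons are the ones where bioimpedance stands apart.

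A third concerns direction. With equal residues the contrast runs opposite to the true effect, and a reader might infer that it always does. The unequal-residue example shows otherwise.

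Finally, section d could be read loosely as meaning before sessions within each phase. That would supply pre-dialysis values, but it is not what the text says, and the post-dialysis line would still have no reading.

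**Conclusion.** The point holds as a conflict between a stated measurement schedule and a stated analysis on a named objective. Under section d as written, 0 of the 4 HDFol versus HDx bioimpedance comparisons has a within-patient on-treatment pair, and no readable text schedules a post-dialysis reading. This does not depend on where the washout lies.

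That the expected labelled contrast is zero whatever the treatment effect rests on three assumptions: washout between the phases, complete washout, and balanced sequences. With incomplete washout, the contrast does not estimate the treatment difference, and nothing firmer can be said about its size or sign.

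This should be fixed. Confidence is medium, because Figure 1 could reduce the matter to a correction of wording in section d.

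**What to change.** 1. Check Figure 1. If it shows on-treatment and post-session bioimpedance readings, amend section d to match it. The cost is a wording change.
2. Otherwise, amend section d to add a pre-dialysis bioimpedance reading at the last session of each phase, which section e already uses for blood sampling. Base the HDx versus HDFol comparison on those readings, and keep the pre-phase readings as period baselines and as the high-flux reference. The last session is a reasonable anchor rather than one the documents dictate; its merit is that the patient has by then been treated and is already being sampled.
3. For the post-dialysis bioimpedance line, either schedule a post-session reading at those same sessions or delete the line from the analysis list.
4. Make section d, Figure 1 and the analysis list agree.

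Step 2 adds two short, non-invasive readings per patient on the same device (3 become 5). Post-session readings on both modalities make it four extra (3 become 7). If the post-dialysis comparisons with high-flux HD are kept, one further post-session reading on high-flux HD is needed (8). The burden is staff time and the recumbent measurement; the HDx and HDFol readings fall at sessions already attended.

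### The randomized HDFol versus HDx comparison is planned as a plain paired test that ignores period; analysing it by sequence is a cheap improvement

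*Combined protocol and SAP*

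**What the plan says.** The Objectives state that the two modalities will be compared "through a prospective, randomized and cross-over study". The Hypothesis section adds: "Our hypothesis is that HDx is noninferior to olHDF in the following parameters", namely hemodynamic stability, nutritional and fluid status, and beta-2 microglobulin removal. The title calls the trial a "PILOT STUDY ON INTRADIALYTIC HEMODYNAMICS AND FLUID STATUS".

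The Statistical Analysis section gives one rule for everything. Depending on distribution, a "paired t test or Wilcoxon's test will be used, respectively". It is applied to HDFol versus HDx, HDFol versus high-flux HD, and HDx versus high-flux HD. Only the first of these is a contrast between randomized periods. High-flux HD is background care: "Before initiating protocol and during the washout period, patients will be submitted to high-flux HD" (Concise methods, b) Dialysis).

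The text mentions no period effect, sequence effect or sequence-specific analysis. It gives no sample size, allocation scheme, noninferiority margin or decision rule.

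**The concern.** Pairing removes differences between patients. It does not remove a change between the first and second period, for example from season, staff, laboratory drift or the course of the disease. In a two-period crossover such a change adds to the HDx minus HDFol difference in one sequence and subtracts from it in the other.

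Two things follow if a period effect exists. With equal sequences the change cancels in the mean but stays in the variance, so intervals are too wide and noninferiority is harder to show. With unequal sequences, through chance or dropout, part of the change stays in the estimate and can favour either modality. Because the hypothesis is noninferiority, the direction matters: a bias towards HDx raises the chance of a false noninferiority claim, and the two-sided error does not reveal it.

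**Working it through.** **Inputs.** The plan has no figure to reproduce. From the documents: the randomized crossover, the noninferiority hypothesis and the paired test. Assumed: N = 16, a true effect of 0.8 for power, two-sided alpha 5%, noninferiority read from the 95% CI (so 2.5% one-sided), no carry-over, and period shifts of 0 to 0.5. The unit is the SD of the paired difference within a sequence.

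**Model.** The paired difference HDx − HDFol has mean effect + shift in one sequence (n1 patients) and effect − shift in the other (n2), with SD 1.

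**Step 1: bias of the paired estimate** = shift × (n1 − n2)/N.
- 8:8: 0.
- 9:7: 0.25 × 2/16 = 0.03 and 0.5 × 2/16 = 0.06.
- 10:6: 0.25 × 4/16 = 0.06 and 0.5 × 4/16 = 0.125.

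**Step 2: overstatement of the standard error, equal sequences** = √(1 + shift² × N/(N − 1)). From N = 10 to N = 40 the ratio runs from 1.034 to 1.032 at shift 0.25, and from 1.130 to 1.121 at shift 0.5. At shift 0.1 it is about 1.005.

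**Step 3: paired t test.** The mean is N(effect + bias, 1/N). The sum of squares is noncentral chi-square on N − 1 df with noncentrality shift² × 4·n1·n2/N. Numerical integration gives the results below.

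**Step 4: sequence-based t test.** SE = √(1/n1 + 1/n2)/2 on N − 2 df. At 8:8 the SE is 0.250 and the noncentrality 0.8/0.250 = 3.2. At 10:6 the SE is 0.258 and the noncentrality 0.8/0.258 = 3.10. Power is 84.5% and 82.1%, whatever the shift, and the one-sided error is 2.5%.

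| Split | Shift | Paired: one-sided error, shift favours / opposes HDx | Paired: power | Sequence-based: power |
|---|---|---|---|---|
| 8:8 | 0 | 2.5% | 84.8% | 84.5% |
| 8:8 | 0.25 | 2.2% | 83.2% | 84.5% |
| 8:8 | 0.5 | 1.5% | 78.0% | 84.5% |
| 10:6 | 0 | 2.5% | 84.8% | 82.1% |
| 10:6 | 0.25 | 3.8% / 1.2% | 88.4% / 76.9% | 82.1% |
| 10:6 | 0.5 | 4.4% / 0.4% | 89.4% / 62.9% | 82.1% |

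At 9:7 the one-sided error is only 2.9% and 2.6% at shifts 0.25 and 0.5 favouring HDx. At 10:6 and shift 0.5 the two-sided error is 4.4% + 0.4%, or 4.9% before rounding, which looks correct and hides the asymmetry.

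**Step 5: how often the harmful split arises.** Suppose sequences were assigned by simple randomization, with X ~ Bin(16, 0.5). Then P(X ≥ 10) = 14,893/65,536 = 22.7% in the direction that favours HDx, and the same in the other.

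**Step 6: average over all splits under that scheme.** The paired test's one-sided error is 2.50% at shift 0.25 and 2.51% at 0.5. Average power, paired versus sequence-based, is 84.8% vs 81.8% at shift 0, 84.5% vs 81.8% at 0.1, 82.7% vs 81.8% at 0.25, and 76.2% vs 81.8% at 0.5.

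**The case against.** The strongest reply is that the paired test is valid over the randomization. If each patient's order is a fair coin toss, the paired differences are independent draws centred on the true effect, and Step 6 shows that the error rate hardly moves. A reader might infer from the 4.4% that the plan inflates the trial's false-noninferiority rate. The documents do not support that: the figure holds only for a realized 10:6 split with a shift of 0.5 SD in the direction that favours HDx. Nor should it be set beside the 45% probability of a 10:6 or worse split, because that counts both directions. What stands against the reply is the conditional argument: once the split is known to be unequal, a period shift biases the estimate by a known formula, and the analysis can remove it.

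The reply is also right that nothing in the text suggests a period effect. Patients are on maintenance dialysis and return to high-flux HD in the washout. Figure 1 is not available and may show sequences or allocation, although a design figure would not add a period term to the stated test. With small shifts and unbalanced sequences, adjustment loses power. And because no margin is stated, neither test alone can establish noninferiority.

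A second tempting inference is that first-session and last-session values are pooled. The methods schedule blood sampling in both sessions of each phase, and the analysis section does not say which is used. That is missing detail, not a stated pooling, and Figure 1 may settle it.

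**Conclusion.** The point holds in a limited form. The randomized contrast is analysed without regard to period. If a period effect exists, the cost is lost precision with equal sequences and, conditional on an unequal split, a bias of shift × (n1 − n2)/N. With equal sequences the loss is small up to about 0.25 SD (1.6 power points at 8:8) and reaches 6.8 points at 0.5 SD (84.8% to 78.0%). There is essentially no inflation of error averaged over simple randomization.

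All sizes rest on assumed N, allocation, SD, period shift and decision rule. For a pilot the harm is minor, so this is a change to consider, not a flaw that undermines the trial. Which session supplies each value, and which sample supplies the high-flux value, are clarifications outside this conclusion.

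**What to change.** For HDFol versus HDx, compute each patient's period difference (period 2 minus period 1) and compare it between the two randomized sequences with a two-sample t test. Half the difference in means, signed as HDx minus HDFol, estimates the treatment effect; report it with its 95% CI. If the differences are not normal, use the rank-sum test on the same values and report half the Hodges-Lehmann shift with its CI, so that an interval exists in either case.

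Keep the paired test for the two comparisons with high-flux HD, which is not a randomized period, and label them before-after. As clarifications, name the session that supplies each value and the sample that supplies the high-flux value.

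The cost is SAP wording and no new data. With balanced sequences it is one degree of freedom (84.8% to 84.5% power at 8:8). With unbalanced sequences the variance also rises by N²/(4·n1·n2): 256/240 = 1.067 at 10:6. With no period effect that loses 2.7 points (84.8% to 82.1%), and the average loss over simple randomization at N = 16 is about 3 points (84.8% to 81.8%). For ranks at 10:6 with no period effect, simulated power falls from 82% (signed-rank) to 77% (rank-sum); at 8:8 both are 82%. Balanced allocation of sequences keeps the cost near zero.
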